9.4 Summary of treatment group comparability

Demographic and baseline characteristics and disease characteristics will be summarized and compared between the treated subjects and the subjects from matched control group(s) for the ITT and the PP populations.

9.5 Methods of analysis

9.5.1 Effectiveness

The ITT Population will be used for all effectiveness analyses. Selected analyses may also be performed using the PP population. Effectiveness analyses will be presented for the overall populations and by subgroup of subjects (e.g. cause of chronic pain), as appropriate.

9.5.1.1 Change in baseline pain NRS

The change in baseline pain NRS will be defined as the difference between chronic pain state at the beginning of the study versus the end of the study (after 3 years of treatment).

The primary analysis will be a difference analysis with comparison to appropriately selected matched controls. The endpoint will be tested using a two-sided z-test test to compare results between the prospectively enrolled treated participants and external matched controls. The impact of confounding factors will be reduced as much as possible by including values of important covariates in the model and by performing sub-analyses. Covariates included in the model will be selected based on:

- (1) Base line pain scores
- (2) Cannabis consumption experience and/or
- (3) Cause of chronic pain

A propensity score analysis may also be performed to match subjects between the treated and matched control groups. The propensity score is the probability of treatment assignment conditional on observed baseline characteristics. Propensity score matching entails forming

matched sets of treated and untreated participants who share a similar value of the propensity score (Rosenbaum PR & Rubin DB, 1983a and 1985).

Secondary measure outcome variables

Descriptive statistics will be presented for Quality of life changes, sleep NRS changes, Anxiety changes, confusion changes, dizziness changes, and changes in the use of concomitant medicines. Change from baseline to a number of analysis time points (including 12 months) will be assessed. Repeated measures analyses will be undertaken to allow for the evaluation of outcomes at any timepoint. In addition, multi-state modelling (MSM) will be undertaken to assess time-varying confounds. These will be described in detail in the SAP.

A comparison between treated subjects and matched control may be performed if similar endpoints are collected in both databases. Time to event analysis, multiple regression analysis for continuous and/or categorical outputs and/or propensity score analysis may be performed as appropriate.

To deal with missing data in subjects over the 3 year period, patterns of missingness will be evaluated including missing completely at random (MCAR), missing at random (MAR) or missing not at random (MNAR) will be assessed, this will be described in detail in the SAP.

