5. STUDY OBJECTIVES

- The primary objective is to evaluate the effectiveness of the treatment regimen on reducing the average intensity of pain of subjects with chronic non-cancer pain compared to matched controls.
- The secondary objective is to evaluate the effectiveness of the treatment regimen on quality of life measurement, global impression of change, well-being, appetite, sleep scores and changes in concomitant medicine of chronic non cancer pain sufferers compared to matched controls.
- Safety and tolerability of the treatment regimen in chronic non-cancer pain subjects will also be assessed.

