Full details, including the use of the matched control database(s), of the interim and final statistical analyses to be performed will be described in detail in the Statistical Analysis Plan (SAP). The SAP will be developed to specify the statistical methods to be used and it will be finalized prior to the final or interim data cut-offs.

The progress of each subject identified for participation in the trial will be documented in a flowchart so that all subjects are accounted for, whether or not they go on to enter the trial itself. This flowchart will also show the number of subjects with data available as well as the incidence of withdrawal from treatment. All data obtained in this study will be presented in individual subject data listings.

The analyses will be exploratory and primarily make use of descriptive statistical methods. Tabulations will be produced for appropriate effectiveness and safety parameters. For categorical variables, summary tabulations of the number and percentage of participants within each category (with a category for missing data where applicable) of the parameter will be presented. For continuous variables, the number of participants, mean, standard deviation (SD), median, minimum, and maximum values will be presented. Statistics may be presented for cohorts of interest (e.g. by pain type) if sample size permits.

Inferential statistical methods will only be employed to highlight interesting aspects of the data. Any p-values will be interpreted descriptively; no adjustment for multiple testing to control type-1 error will be done. 95% confidence intervals (CIs) will be presented as appropriate.

Statistical analysis, data listings, graphs and summary tables will be produced using SAS®, version 9.2 or above.

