9.2 Determination of Sample Size

The sample size was calculated based on the objective of showing a greater proportion of patients experiencing an improvement in NRS score, from baseline to 12 months, when using CBMP in addition to the standard of care as compared to the standard of care alone. We assume that 25% of matched controls will experience an improvement in NRS score (O'Brien and Breivik, 2011). A sample size of 3600 patients using CBMP plus 3600 matched controls will provide at least 80% power to detect an increase in the proportion of patients experiencing a 28% improvement, using a two-sided z-test test for proportions with a Type I error rate of 5%. After adjusting for 10% non-evaluable rate and a 20% match failure rate, the sample size is 5000 CBMP patients plus 5000 matched controls.

Thus the null hypothesis $H_0: P=0.8$ is tested against the one-sided alternative $H_1: P>0.80$. Assuming that the expected pain reduction at 18 months for the treated subjects is $P_1=86\%$, a minimum sample size of 500 subjects for each type of chronic pain, with a total minimum number of 5000 subjects, is needed to design the study at 80% power, using a one-sided level 0.05 test for single proportion and the variance from the empirical estimate.

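### The draft CANPAIN protocol sizes the study on a 12-month pain responder proportion but fixes the primary pain change at 3 years, so the stated 80% power does not belong to the stated primary analysis

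*Protocol*

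**What the plan says.** All references are to the draft CANPAIN protocol in Appendix 1, unless stated otherwise.

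- **Section 9.2, first paragraph.** The sample size rests on "showing a greater proportion of patients experiencing an improvement in NRS score, from baseline to 12 months". The inputs are 25% improved among controls, a 28% figure for CBMP, a two-sided 5% z-test for proportions, and 3600 evaluable per group for at least 80% power. "After adjusting for 10% non-evaluable rate and a 20% match failure rate", the total is 5000 per group.
- **Section 9.2, second paragraph.** A separate one-sided 5% test of a single proportion, 80% against 86%, is added: "Assuming that the expected pain reduction at 18 months for the treated subjects is" 86%. It asks for 500 subjects per pain type.
- **Section 9.5.1.1.** Change in pain NRS is "the difference between chronic pain state at the beginning of the study versus the end of the study (after 3 years of treatment". The next sentences make the primary analysis a difference analysis against matched controls: "The endpoint will be tested using a two-sided z-test test". The 12-month point appears only under the secondary outcome variables: "Change from baseline to a number of analysis time points (including 12 months) will be assessed".
- **Section 5.** The primary objective concerns the "effectiveness of the treatment regimen on reducing the average intensity of pain", again against matched controls.
- **Section 9.1.** The analyses are called exploratory, and of the SAP it is said that "it will be finalized prior to the final or interim data cut-offs".

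**The concern.** A power statement is useful only for the analysis it describes. Here the sample size section and the primary analysis section name different time points for the same pain outcome, and the second calculation in 9.2 adds a third (18 months).

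The type of outcome probably differs too. Section 9.2 counts patients who improve, whereas sections 5 and 9.5.1.1 speak of pain intensity and of a change in NRS. This is less certain, because the z-test in 9.5.1.1 repeats the wording of 9.2 and could be meant for proportions. The time-point conflict does not depend on it.

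What is at stake is the justification for enrolling 10,000 people. It applies to a result the draft does not name as primary. The 10% non-evaluable allowance belongs to the 12-month calculation, and nothing in the draft says it would hold at 3 years.

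**Working it through.** **1. The plan's own figure (12 months).** Inputs from 9.2: p1 = 0.25, p2 = 0.28, two-sided 5%, z-test with pooled null variance.

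n = [1.960 √(2 × 0.265 × 0.735) + 0.842 √(0.25 × 0.75 + 0.28 × 0.72)]² / 0.03² = 3397 per group.

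Power at n = 3600: Φ[(0.03 × √3600 − 1.960 × 0.6241) / 0.6238] = Φ(0.925) = 82.2%.

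Inflation: 5000 × 0.8 = 4000 matched pairs, and 4000 × 0.9 = 3600 evaluable.

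The claim of at least 80% power is therefore correct for these inputs. The wording around 28% is ambiguous, and it could be read as a size of improvement. Reading it as the treated proportion is the only interpretation tried that fits 3600: a 28% relative increase (25% v 32%) needs 652 per group, and an increase of 28 percentage points (25% v 53%) needs 47.

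**2. What is available for the primary analysis as written (3 years).**

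| Input needed | 12 months (9.2) | 3 years (9.5.1.1) |
|---|---|---|
| Control and treated response rates | 25%, 28% | not given |
| Non-evaluable rate | 10% | not given |
| SD and target difference, if a mean change | not applicable | not given |

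Power for the 3-year analysis cannot be computed from the document.

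**3. Illustration only.** Assumptions: the 12-month proportions carry over to 3 years; 20% match failure; lost pairs drop out of the analysis; losses are applied once per pair, as 9.2 does.

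| Total non-evaluable at the primary time point | Pairs left | Power |
|---|---|---|
| 10% (as in 9.2) | 3600 | 82% |
| 19% (10% a year for 2 years) | 3240 | 78% |
| 27.1% (10% a year for 3 years) | 2916 | 74% |
| 40% | 2400 | 65% |

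Under these assumptions 80% power survives a loss of up to 4000 − 3397 = 603 pairs. That is 15.1% in total, or 1 − (3397/4000)^(1/3) = 5.3% a year over 3 years. Keeping 3600 pairs at 3 years with 10% loss a year would need 3600/(0.8 × 0.729) = 6173 per group.

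**4. If the primary outcome is a mean change.** With an assumed SD of 1.5 to 3.0 points, 3600 per group have 80% power for a difference of 2.80 × SD × √(2/3600), which is 0.10 to 0.20 NRS points. This is a different quantity from 25% v 28%.

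**5. The second calculation in 9.2.** For 80% v 86%, one-sided 5% and 80% power, n = 251 with the null variance at the critical value, or 207 with the alternative variance only. The stated 500 per pain type has 97.6% or 98.7% power respectively (exact binomial 96.7%). It has no control group and a different time point, so it supports neither the two-group calculation nor the primary analysis.

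**The case against.** The strongest case is about weight. The study actually being run is the 3-month feasibility study, which has no efficacy endpoint and no power claim. The appended protocol is marked as a draft, received a non-acceptance opinion, and is to be followed by a new application (feasibility protocol, section 2). Within it, 9.1 calls the analyses exploratory, with p-values read descriptively, so no confirmatory decision rests on the power figure. This stands and limits the consequence. It does not remove the contradiction: 9.2 still states a power and a type I error rate, and 9.5.1.1 still names a primary two-sided test.

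It can also be said that 12 months was evidently intended. The synopsis ties the 5000 to participants with at least 12 months of treatment, and 9.5.1.1 provides repeated measures analyses at any time point. That makes the likely repair short, but neither place names 12 months as primary. The synopsis also treats 5000 as a count of people who have completed 12 months, whereas in 9.2 it is the number before losses.

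Leaving the matter to the SAP would not help. The protocol itself fixes both time points, so a SAP that chose either would contradict one section. Because the SAP is to be final before the data cut-offs, choosing the result after seeing the data is not the worry.

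The attrition figures are fairly open to challenge. The 10% yearly loss is assumed, section 6.4.8 keeps following subjects who stop treatment, the analysis is by intention to treat, and missing-data handling is left to the SAP. Actual loss could be lower. Conversely, if 10% applied to each member of a pair independently and complete pairs were required, 4000 × 0.81 = 3240 pairs would remain even at 12 months. The figures show sensitivity and are not an estimate.

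**Conclusion.** The concern holds, and the text is wrong as written. The power of at least 80% and the 5000 per group are correctly calculated for a 12-month proportion (82% at 25% v 28%), but 9.5.1.1 makes a 3-year pain change primary, and no other section reconciles the two. The time-point conflict is explicit; the mismatch in outcome type is probable. Power at 3 years is unknown and could be at or above 80%. It falls below that only if, with unchanged proportions, total loss exceeds about 15%.

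This should be fixed before the new application. It has no bearing on the conduct or results of the feasibility study.

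**What to change.** - State the same primary endpoint, improvement threshold and time point in sections 5, 9.2 and 9.5.1.1. The simplest choice is to make the 12-month proportion already sized in 9.2 primary, with the 18-month and 3-year changes secondary.
- If a mean NRS change or the 3-year time point is kept as primary, restate the power in 9.2 for it, giving the expected rates or the SD and target difference, and the non-evaluable rate at that time.
- Say plainly in 9.2 what the 28% is.
- Delete the 18-month single-proportion calculation or label its purpose.
- Reconcile the follow-up statements so that the primary time point can be observed for every enrolled participant: the synopsis, 3.1 (a maximum of 3 years per participant), 6.1 (3 years each, ending after the last subject's 3 years), 6.3 (study duration 3 years) and 8.1 (a five-year date).

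**Cost.** With 12 months as primary, only wording changes, since pain NRS is already collected weekly (6.6.1). The price is that 3-year durability becomes a secondary claim and the objective in section 5 is reworded. With 3 years as primary, the stated power or the sample size will have to change.

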6.2 Discussion of study design and choice of control groups

The aim of the study is to evaluate whether the addition of medical cannabis to standard of care or at the completion of standard of care is beneficial with regards to pain scores, quality of life, quality of sleep and changes in the use of concomitant medication, as well as being safe and tolerable in subjects suffering from chronic non-cancer pain. The study will utilise a combination of patient reported outcomes and data from the NHS (chronic pain diagnosis, standard of care and health related laboratory tests) to provide a holistic evaluation of the CBMP treatment when combined with standard of care. The patient reported outcomes and NHS data will be transferred into an electronic health repository which will manage their day to day care, provide reports and alerts on the tolerability of the cannabis for each subject and will form the clinical trial database. The matched controls will exclude those potential participants who are consuming illicit cannabis, identified by drug screening. If participants are using illicit cannabis, they will be given the option to stop with a 3-week wash out period. If participants are not willing to cease, they will not be eligible for inclusion in the matched control cohort.

Controls

The analyses of effectiveness will be conducted through comparison with matched controls obtained from NHS sites established to enable data collection from consented subjects receiving standard of care only. Subjects who consent to have their data collected will be asked to provide essential demographic information, details on their chronic pain type, their standard of care and whether they are currently using medical cannabis to help with their pain. This information will be used to match the subject to subjects on the trial. The data collected in the match cohort will mirror the data collected from the CANPAIN minus tolerability data which will not be required.

The CANPAIN study will follow a pragmatic, real-world, 'all-comers' design with wide inclusion criteria, which is designed to result in a more representative sample of the target population and of the matched controls. Baseline characteristics of treated participants may still differ systematically from those of the matched control group and one must account for these systematic differences when estimating the effect of treatment on outcomes.

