6.6.1 Assessments during the study

- **Initiation visit/call (Day 0)**

Day 0 (baseline) for each subject will be the initial clinic visit when treatment is started. Alongside the daily monitoring of CBMP tolerability through the patient reported outcomes,

subjects will have 3 monthly consultations..

- Complete medical questionnaire form
- Review of medical history and relevant investigations
- Review current treatment being received or proposed
- Assess inclusion and exclusion criteria
- Written informed consent obtained
- Discuss the medicinal cannabis therapy
- Go through dosing instructions with participants (i.e., how to use the device, when to use the CBMP and how to enter data onto their smart device).
- If appropriate arrange the prescription

Daily assessments (concomitant with dosing)

- Tolerability NRS measurements (anxiety, drowsiness, dizziness, shortness of breath)

The tolerability measures collected 30 minutes after dosing with the CBMP are collected and fed back to Heydoc. Any NRS score >5 causes an alert, which triggers a study physician to contact the subject to assess their status and to elicit an appropriate response.

Weekly assessments

- Efficacy NRS measurements (pain, well-being, sleep quality, fatigue, nausea, depression, appetite)
- Global impression of change

3 monthly assessments

- Quality of life (SF-12)

3 monthly visits/call

- Review of efficacy and tolerability of medicinal cannabis and establishing the subject's overall impression on how they have responded to the CBMP
- Review current treatment being received or proposed
- Adverse events
- Renew prescriptions. Remind the participants of dosing instructions

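### CANPAIN's primary pain outcome is a two-point difference although pain NRS is scheduled weekly; averaging the closing weeks would narrow the confidence interval and mainly help the pain-type subgroups

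*Protocol*

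**What the plan says.** All references are to the CANPAIN protocol in Appendix 1.

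- **Primary outcome (9.5.1.1).** The change in pain NRS is "the difference between chronic pain state at the beginning of the study versus the end of the study", with the end set at 3 years. It is compared with matched controls by a two-sided z-test. "Base line pain scores" head the list on which covariates will be selected.
- **Objective (section 5).** The primary objective concerns "reducing the average intensity of pain of subjects with chronic non-cancer pain compared to matched controls".
- **Frequency (6.6.1).** The weekly assessments are headed by "Efficacy NRS measurements (pain, well-being, sleep quality, fatigue, nausea, depression, appetite"). Table 1-1 also marks the NRS pain row at baseline, weekly and at the three-monthly follow-up.
- **Baseline (6.6.1).** "Day 0 (baseline) for each subject will be the initial clinic visit when treatment is started". No weekly series before treatment is scheduled.
- **Controls (6.2).** "The data collected in the match cohort will mirror the data collected from the CANPAIN minus tolerability data".
- **Use of the intermediate scores (9.5.1.1).** "Repeated measures analyses will be undertaken to allow for the evaluation of outcomes at any timepoint". This sentence stands under the secondary outcomes, with details left to the SAP.

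**The concern.** Three years of weekly scores is about 3 × 52 = 156 pain readings per patient, scheduled for treated patients and, in principle, for controls. The primary definition names two points and makes no use of the rest.

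Chronic pain varies from week to week. A single closing score carries all of that variation, while a short average carries less of it at no cost in data collection. What is at stake is the width of the confidence interval for the primary difference. Section 9.1 treats p-values descriptively and presents 95% intervals, so the interval is the main product. Precision matters most in the pain-type subgroups, where the numbers are much smaller.

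**Working it through.** **The plan's own power figure.** Section 9.2 gives 3600 per group, two-sided 5%, a 25% control rate and at least 80% power. Reading 28% as the treated rate, the standard error is √[(0.25×0.75 + 0.28×0.72)/3600] = 0.0104. With the pooled null variance, power is 82.2%, which agrees with the text. The inflation also reproduces: 3600/(0.9 × 0.8) = 5000. This calculation is for a proportion improved at 12 months, not the 3-year change, so its 80% serves below only as a reference level.

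**Assumed inputs.** The protocol gives no SD of NRS, weekly correlation or NRS effect size. I assume:
- correlation between nearby weekly scores, ρ: 0.6 to 0.9;
- correlation of a closing score with baseline, r: 0.3 to 0.5;
- the four closing weeks exchangeable, the groups treated as independent, and normal approximations.

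**Closing score adjusted for baseline.** Only the closing end is averaged, so the single Day 0 baseline suffices. Residual variance, in units of the score variance, is:
- one closing score: 1 − r²
- mean of four: (1 + 3ρ)/4 − r²

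With the ratio of the second to the first, a test with 80% power on one score has power Φ(2.80/√ratio − 1.96) on the mean of four. Interval width scales with √ratio.

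| ρ | r | Ratio | Interval narrower by | Power from 80% |
|---|---|---|---|---|
| 0.6 | 0.5 | 0.45/0.75 = 0.60 | 23% | 95% |
| 0.7 | 0.5 | 0.525/0.75 = 0.70 | 16% | 92% |
| 0.8 | 0.5 | 0.60/0.75 = 0.80 | 11% | 88% |
| 0.8 | 0.3 | 0.76/0.91 = 0.835 | 9% | 87% |
| 0.9 | 0.3 | 0.835/0.91 = 0.918 | 4% | 83% |

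**Unadjusted change score.** Let f be the weekly-noise share of the variance (10% to 30%) and c the correlation of the underlying states (0.3 to 0.7). The variance of change is 2(1 − f)(1 − c) + 2f with single readings. It is 2(1 − f)(1 − c) + f + f/4 when the last four weeks are averaged.
- f = 0.1, c = 0.3: 1.385/1.46 = 0.949, power 80% to 82%.
- f = 0.3, c = 0.7: 0.795/1.02 = 0.779, power 80% to 89%.

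The gain is about 2 to 9 points. Averaging both ends would give 84% to 96%, but that needs pre-treatment weekly scores that are not scheduled.

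**Responder version.** Take 25% versus 28% at 3600 per group, with noise at 10% to 50% of the change variance. Averaging at the end only moves 82.2% to between 83% and 88%.

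**Overall comparison at 3600 per group (assumed SD 2 to 3).** The difference detectable with 80% power is 2.80 × SD × √(2/3600), or 0.13 to 0.20 NRS points. At a true difference of 0.3 points, power is already 98.9% (SD 3) to 100% (SD 2). There is almost no power left to gain, although the interval still narrows.

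**Pain-type subgroup.** Section 9.2 names 500 subjects per pain type. Applying its 10% and 20% losses leaves 500 × 0.9 × 0.8 = 360 per group. With an assumed SD of 3 and a difference of 0.5:
- r = 0.3: residual SD 3√0.91 = 2.86, standard error 2.86√(2/360) = 0.213, power Φ(2.34 − 1.96) = 65%. With the 4-week mean: 69% (ρ 0.9) to 82% (ρ 0.6).
- r = 0.5: residual SD 3√0.75 = 2.60, standard error 0.194, power Φ(2.58 − 1.96) = 73%. With the 4-week mean: 78% (ρ 0.9) to 92% (ρ 0.6).

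**The case against.** **A single closing score is an inference.** Section 9.5.1.1 speaks of a pain state, not of one week's NRS, and section 5 speaks of average intensity. The SAP, to which section 9.1 defers full details, could define a window. This stands as a limit on the claim. It does not remove the point: the two-point definition is fixed in the protocol, and the deferrals within 9.5.1.1 come in the secondary-outcome and missing-data paragraphs.

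**The longitudinal data are not ignored.** Repeated-measures analyses are planned, so a mixed-model primary would largely promote existing work. That is true, but under the secondary heading they do not determine the primary comparison.

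**Two stronger readings are tempting and unsupported.** A reader might infer that the design loses a known 3 to 15 points of power. Every correlation behind such a range is assumed, the 80% start belongs to a 12-month proportion, and the overall comparison has about 99% power or more at 0.3 points under SD 2 to 3. A reader might also infer that one missed final entry removes a patient's endpoint. The protocol does not say so: it adopts an ITT approach, leaves missing-data handling to the SAP, and bars no use of adjacent scores.

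**Limited consequence.** The analyses are described as exploratory. The appendix is a draft of a future study, and the feasibility study being run has no efficacy endpoint. This lowers the urgency, but the draft is still open to change before resubmission.

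**Conclusion.** The point holds in conditional form. The primary outcome is a two-point difference, the intermediate weekly scores are scheduled in treated patients and intended in controls, and the primary definition does not use them. If the closing point is one score, a 4-week closing mean with baseline adjustment would cut residual variance by 8% to 40%. The main benefit is narrower intervals and better power within pain types; the overall comparison gains little power unless the true difference is near the detection limit. The direction follows from the design. The size rests entirely on the assumed correlations and SDs, which the protocol does not supply. It is a worthwhile, nearly free improvement and not an error that invalidates the primary analysis.

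**What to change.** First reconcile the primary time point: section 9.2 uses 12 months in one calculation and 18 months in another, while 9.5.1.1 uses 3 years. Without that, an averaging window has no anchor.

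Then, in 9.5.1.1, define the primary outcome in one of two ways:
- the mean of all available weekly pain NRS scores in the last 4 weeks up to the primary time point, adjusted for Day 0 NRS; or
- the between-group contrast at that time point from a mixed model on all weekly scores.

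Apply the same window or model to the matched controls.

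The cost, once the time point is settled, is one sentence in 9.5.1.1 and a matching one in the SAP. No new data collection is needed. The small downside is that the endpoint then describes a 4-week window and not a single date.
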